6.1 Demographics and Baseline Characteristics

Demographic and baseline characteristics information will be collected at the Baseline visit of the study and will be summarized for the FAS. The number of observations, mean, standard deviation, median, minimum and maximum will be summarized for continuous variables. Categorical or discrete variables will be summarized via frequencies and percentages. Summary statistics will be computed for each treatment group and overall.

Main Demographic and Baseline Characteristics

- Sex (male/female)
- Age (years)
- Age Categories (< 40, [40, 65), ≥ 65 years)
- Race (White, Black or African American, American Indian or Alaska Native, Native Hawaiian or Other Pacific Islander, Asian, Other)
- Geographic Region (North America, South/Central America, Western Europe, Eastern Europe, Asia, Other)
- Ethnicity (Hispanic or Latino, Not Hispanic or Latino)
- Weight (kg)
- Weight Categories (< 60 kg, ≥ 60 kg)
- Height (cm)
- Body Mass Index (BMI) (kg/m²)
- Body Mass Index (BMI) Category (kg/m²) (BMI < 25 vs BMI ≥ 25)

RA Medical History and Characteristics

- Duration of RA Symptoms in years
- Duration of RA Diagnosis in years
- Duration of RA Diagnosis Categories (< 5 year or ≥ 5 year)
- Prior bDMARD use (Yes or No)
- Oral steroid use at baseline (yes, no)
- Oral steroid dose (prednisone equivalent) at baseline
- MTX dose at baseline
- Baseline MTX dose categories (< 15 mg/week or ≥ 15 mg/week)

ACR and/or DAS Components at Baseline

- Tender joint count (TJC68) defined as the number of tender joints out of 68 assessed joints

- Swollen joint count (SJC66) defined as the number of swollen joints out of 66 assessed joints
- Tender joint count (TJC28) defined as the number of tender joints out of 28 assessed joints used for DAS28 calculation
- Swollen joint count (SJC28) defined as the number of swollen joints out of 28 assessed joints used for DAS28 calculation
- Physician's global assessment of disease activity (mm on a 100-mm horizontal visual analogue scale [VAS])
- Patient's assessment of pain within last week (mm on a 100-mm horizontal (VAS)
- Patient's global assessment of disease activity within last 24 hours (mm on a 100-mm horizontal VAS)
- Health Assessment Questionnaire Disability Index of the (HAQ – DI) (range: 0 to 3)
- High sensitivity C-reactive protein (hsCRP) (mg/L)
- Erythrocyte sedimentation rate (ESR) (mm/hr)

Other Baseline RA Disease Characteristics

- Anti-cyclic citrulliated peptide (Anti-CCP) (units)
- Anti-CCP status: Positive or Negative
- Rheumatoid Factor (RF) (units)
- Rheumatoid Factor (RF) status: Positive or Negative
- RF and Anti-CCP both positive vs. at least one negative
- RF and Anti-CCP both negative vs. at least one positive
- DAS28 [hsCRP]
- DAS28 [ESR]
- DAS28 Categories:
 - DAS28 > 5.1 (High Disease Activity)
 - DAS28 ≤ 5.1
- Clinical Disease Activity Index (CDAI)

- CDAI categories:
 - CDAI > 22 (High Disease Activity)
 - CDAI ≤ 22
- Simplified Disease Activity Index (SDAI)
- SDAI categories:
 - SDAI > 26 (High Disease Activity)
 - SDAI ≤ 26
- Radiographic related endpoints:
 - Modified Total Sharp Score (mTSS)
 - Joint erosion score
 - Joint space narrowing score

Patient Report Outcomes at Baseline

- Morning stiffness (severity and duration)
- Functional Assessment of Chronic Illness Therapy-Fatigue (FACIT-F)
- Work Instability Scale for Rheumatoid Arthritis (RA-WIS)
- EQ-5D-5L
- 36-Item Short Form Health Survey (SF-36) Version 2: physical component summary, mental component summary and the 8 sub-domain scores

Clinical Tests at Screening

- Chest x-ray
- ECG
- Tuberculin PPD skin test, QuantiFERON TB Gold test
- Serum pregnancy test

Immunization History

- BCG immunization
- Herpes Zoster immunization

- Hepatitis B immunization

Tobacco/Nicotine and Alcohol Use

- Tobacco/Nicotine Use [user, ex-user, non-user, unknown]
- Alcohol Use [drinker, ex-drinker, non-drinker, unknown]

6.2 Medical History

Medical history data will be summarized and presented for FAS population using body systems and conditions/diagnoses as captured on the CRF. The body systems will be presented in alphabetical order and the conditions/diagnoses will be presented in alphabetical order within each body system. The number and percentage of subjects with a particular condition/diagnosis will be summarized for each randomized treatment group as well as overall. Subjects reporting more than one condition/diagnosis within a body system will be counted only once for that body system. No statistical comparison will be performed for medical history reporting.

6.3 Prior Treatment and Concomitant Medications

Prior and concomitant medications will be summarized by each randomized treatment groups as well as overall for FAS. Prior medications are those medications taken prior to the first dose of study drug. This includes medications with a start date before the first study drug administration date, regardless of the end date of these medications. Medications taken on the day of the first dose of study drug are not counted as prior medications. Concomitant medications are those medications, other than study drug, taken after the first dose of study drug and within 14 days of the last dose of study drug. This includes medications with a start date between first study drug administration and last study drug administration + 14 days, as well as, medications with a start date prior to first dose of study drug and which are ongoing after first dose of study drug. Medications taken on the day of the first dose of study drug are counted as concomitant medications.

The number and percentage of subjects who received a prior medication and the number and percentage of subjects who received a concomitant medication will be tabulated separately by the generic name assigned by the most current version of the World Health Organization (WHO) Drug Dictionary.

6.4 Protocol Deviations

Protocol deviations based on ICH deviation criteria are categorized as follows:

1. Those who entered the study even though they did not satisfy the entry criteria
2. Those who developed withdrawal criteria during the study and were not withdrawn
3. Those who received the wrong treatment or incorrect dose, and
4. Those who received an excluded or prohibited concomitant medication.

The protocol deviations listed above will be summarized and listed by treatment group.

7.0 Patient Disposition

The following will be summarized by randomized treatment group as well as overall:

- number of subjects randomized,
- number of subjects included in key analysis populations (Full Analysis Set, Per Protocol Analysis Set for primary efficacy analysis, and Safety Analysis Set for short-term safety analysis),
- number of subjects on-going in Period 1 (if applicable),
- number of subjects who completed Period 1 study participation,
- number of subjects who entered Period 2,
- number of subjects who completed overall study (Period 1 and Period 2) participation (if applicable).

This summary will be repeated by site.

Premature discontinuation details will be further summarized separately for Period 1 and Period 2 as follows.

Period 1

The numbers and percentages of subjects completed Period 1 and prematurely discontinued in Period 1 will be summarized, separately by study drug and study participation completion/discontinuation, with the primary reason for discontinuation collected from CRF by the following categories:

- Adverse event (AE)
- Withdrew consent
- Lost to follow-up
- Lack of efficacy
- Other.

Study participation completion/discontinuation will be summarized for Period 1 by randomized treatment group and by treatment group sequence, respectively.

Study drug completion/discontinuation will be summarized as follows:

- By randomized treatment group: number and percentage of completion by Week 14 and by Week 26, number/percentage and primary reason for discontinuation by Week 14 and between Week 14 to Week 26;
- By treatment group sequence: number and percentage of completion by Week 26 and by Period 1, number/percentage and primary reason for discontinuation between Week 14 to Week 26, and between Week 26 to end of Period 1.

Treatment group sequences are defined as:

1. Placebo → Upadacitinib 15 mg QD
2. ADA 40 mg EOW

3. ADA 40 mg EOW → Upadacitinib 15 mg QD
4. Upadacitinib 15 mg QD
5. Upadacitinib 15 mg QD → ADA 40 mg EOW

Subjects may have more than one reason for discontinuing, but only the primary reason will be summarized.

In addition, the number and percentage of subjects enrolled in Period 2 will also be summarized.

Period 2

Period 2 patient dispositions and reason for discontinuation will be summarized for overall and by treatment in Period 2 defined as follows:

1. Upadacitinib 15 mg QD
2. ADA 40 mg EOW

Among the subjects who entered Period 2 participation (regardless of whether subject prematurely discontinued study drug in Period 1), the number and percentage of subjects who completed and who prematurely discontinued study participation in Period 2 will be summarized. Among the subjects who entered Period 2 upon completion of study drug in Period 1, the number and percentage of subjects who completed and who prematurely discontinued study drug in Period 2 will be summarized.

For subjects who prematurely discontinued study drug or study participation, the primary reason for discontinuation will be summarized by the following categories (as collected in CRF):

- Adverse event (AE)
- Withdrew consent

- Lost to follow-up
- Lack of efficacy
- Other.

Subjects may have more than one reason for discontinuing, but only the primary reason will be summarized.

8.0 Study Drug Exposure and Compliance

8.1 Study Drug Exposure

The duration of exposure to study drug will be summarized for the safety analysis set by the following groups. Subjects could switch to another treatment at Week 14 or later per study design. For subjects switching treatments, the exposure under the new study drug begins on the day when the new therapy is initiated, and the exposure under the previous study drug ends on the day before.

The duration of exposure to study drugs will be summarized by the following groups.

1. Placebo
2. ADA 40 mg EOW

This includes ADA exposure from subjects starting on ADA 40 mg EOW and subjects who switched from Upadacitinib 15 mg QD to ADA 40 mg EOW.

3. Upadacitinib 15 mg QD

This includes Upadacitinib 15 mg QD exposure from subjects starting on Upadacitinib 15 mg QD, subjects who switched from placebo to Upadacitinib 15 mg QD, and subjects who switched from ADA 40 mg EOW to Upadacitinib 15 mg QD.

The duration of exposure to study drug will be summarized for each group as specified above, with the number of subjects, mean, standard deviation, median, minimum and

maximum values. In addition, the number and percentage of subjects exposed to study drug will be summarized for the following cumulative duration intervals.

- ≥ 2 weeks
- ≥ 1 month
- ≥ 3 months
- ≥ 6 months
- ≥ 9 months
- ≥ 12 months
- ≥ 18 months
- ≥ 2 years
- ≥ 2.5 years
- ≥ 3 years
- ≥ 4 years

8.2 Compliance

Study drug compliance for Upadacitinib/PBO and for ADA/PBO will be summarized separately for each treatment group up to Week 26. Upadacitinib/PBO compliance is defined as the number of Upadacitinib/PBO tablets taken (i.e., the difference between the number of tablets dispensed and the number of tablets returned) during the subject's participation up to Week 26 divided by the number of days that the subject was in the Treatment Phase up to Week 26. ADA/PBO compliance is defined as the number of ADA injections administered during the subject's participation up to Week 26 divided by the number of injections planned during the subject's participation in the Treatment Phase up to Week 26.

9.0 Efficacy Analysis

9.1 General Considerations

There are three sets of planned efficacy analysis: efficacy analysis by Week 12, efficacy analysis for Period 1, and long-term efficacy analysis. All efficacy analyses will be carried out using the FAS population.

9.1.1 Efficacy Analysis at Different Phases of the Study

Efficacy Analysis by Week 12

Standard efficacy analysis by randomized treatment groups (placebo, ADA 40 mg EOW and Upadacitinib 15 mg QD) will be performed on efficacy data up to Week 12. No protocol-defined treatment switching will occur prior to the time point. Formal statistical inference will be generated, and results from this set of analysis will be used as the key efficacy findings of this study.

Efficacy Analysis for Period 1

For visits at Weeks 14, 18, 22, or 26, subjects may have switched to a treatment that is different from their originally randomized treatment group due to lack of efficacy. At Week 26, all remaining subjects in the original placebo group will be switched to blinded ABT-494 treatment regardless of clinical response. For treatment group comparison purposes, appropriate approaches will be applied to assessments that occur after the time of such treatment switching. For Week 26 reporting, this set of analyses will only be presented up to Week 26.

Long-Term Efficacy Analysis

Long-term efficacy analysis will be performed on As Observed data (defined in Section 9.1.2) by treatment group sequence as described below. There will be no statistical testing; only descriptive statistics and confidence intervals will be provided. For Week 26 reporting, this set of analyses will only be presented up to Week 48.

1. Placebo → Upadacitinib 15 mg QD
2. ADA 40 mg EOW
3. ADA 40 mg EOW → Upadacitinib 15 mg QD
4. Upadacitinib 15 mg QD
5. Upadacitinib 15 mg QD → ADA 40 mg EOW

9.1.2 Definitions of Missing Data Handling Approaches

Non-Responder Imputation (NRI) Approach

The NRI approach will categorize any subject who has missing value for categorical variables at a specific visit as non-responder for that visit. In addition, subjects who prematurely discontinue from study drug will be considered as non-responders for all subsequent visits after discontinuation.

Observed Cases (OC)

The OC analysis will not impute values for missing evaluations, and thus a subject who does not have an evaluation on a scheduled visit will be excluded from the OC analysis for that visit. In addition, OC will not include values after subject have switched study treatment or after premature discontinuation of study drug.

As Observed (AO)

The AO analysis will not impute values for missing evaluations, and thus a subject who does not have an evaluation on a scheduled visit will be excluded from the AO analysis for that visit. Regardless of treatment switching or premature discontinuation of study drug, all observed data will be used in the analysis.

Mixed Effect Model Repeat Measurement (MMRM)

The repeated measure analysis will be conducted using mixed model including observed measurements at all visits. The mixed model includes the categorical fixed effects of

treatment, visit and treatment-by-visit interaction, main stratification factors at randomization, and the continuous fixed covariates of baseline measurement. An unstructured variance covariance matrix will be used. The parameter estimations are based on the assumption of data being missing at random and using the method of restrictive maximum likelihood (REML). [REDACTED]

[REDACTED]

Multiple Imputations (MI)

The MI analysis will impute missing data multiple times under appropriate random variation and thus generate multiple imputed "pseudo-complete" datasets. Results will be aggregated across the multiple imputed datasets, overcoming drawbacks of the single imputation methods. [REDACTED]

[REDACTED]

Linear Extrapolation for Radiographic Data

For radiographic data (i.e., mTSS-based endpoints), linear extrapolation will be applied to subjects who were rescued or prematurely discontinued study drug, where the x-ray at the time point of interest after rescue or PD will be imputed assuming a linear relationship between baseline, the x-ray collected at rescue or PD, and the time point of interest.

To summarize the use of different missing data handling approaches in the analysis:

- For non-radiographic data: The NRI approach will serve as the primary analysis approach for key binary endpoints, while OC will be repeated as a sensitivity analysis. The MI approach will serve as the primary analysis approach for key continuous endpoints HAQ-DI and DAS28 at Week 12. The MMRM will serve as the primary analysis for other key continuous endpoints. The AO analysis will be performed for descriptive summary.
- For radiographic data: Analysis based on both linear extrapolation and AO will be conducted, and linear extrapolation results will be used for the purpose of multiplicity control.
- A missing not at random (MNAR) model that varies assumptions for the missing data in active treatment groups and placebo groups may be used as a sensitivity analysis for key continuous endpoints to account for potential deviation from the MAR assumption.

9.2 Efficacy Analysis by Week 12

9.2.1 Primary Efficacy Analysis

The primary endpoint for US/FDA regulatory purposes is the proportion of subjects achieving ACR20 response at Week 12. The primary endpoint for EU/EMA regulatory purposes is the proportion of subjects achieving CR based on DAS28(CRP) at Week 12. Analyses will be conducted separately for US/FDA regulatory purposes and EU/EMA regulatory purposes; for each set of analysis, only one primary endpoint is specified.

Analysis of the primary endpoint will be conducted on the FAS based on randomized treatment groups. Point estimate and 95% CI using normal approximation will be provided for the response rate for each randomized treatment group. Comparisons of the primary endpoint will be made between the Upadacitinib 15 mg QD group and the placebo group using the Cochran-Mantel-Haenszel test adjusting for stratification factor prior bDMARD use. Point estimate, 95% CI using normal approximation and p-value for

the treatment comparison will be presented. For the primary analysis, non-responder imputation (NRI) will be used.

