##### **8.1.4.1 Efficacy Analysis for Period 1**

###### **8.1.4.1.1 Primary Efficacy Variables**

The primary endpoint in Period 1 (at Week 12) for US/FDA regulatory purposes is listed in Section 5.3.3.1.1. The primary endpoint in Period 1 (at Week 12) for EU/EMA regulatory purposes is also listed in Section 5.3.3.1.1. Analyses will be conducted separately for US/FDA regulatory purposes and EU/EMA regulatory purposes; for each set of analysis, only one primary endpoint is specified.

Analysis of the primary endpoint will be conducted on the FAS based on treatment as randomized. For the ACR20 and CR comparison between the upadacitinib group and the placebo group, Cochran-Mantel-Haenszel test adjusting for main stratification factors will be used. For the primary analysis of ACR20 and CR response at Week 12,

Non-Responder Imputation (NRI) will be used. In addition, sensitivity analysis will be done using Observed Cases (OC). Supportive analysis will also be conducted on the Per Protocol Analysis Set.

The primary efficacy analyses will be performed in demographic subgroups including age, gender, weight, body mass index, race, and geographical region to assess the consistency of the treatment effect. Additional subgroup analyses based on baseline disease characteristics and stratification factors will also be conducted.

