## **8.3 Randomization Methods**

Subjects will be randomly assigned in a 2:2:1 ratio to one of the three treatment groups (Upadacitinib 15 mg QD, placebo and ADA 40 mg eow) stratified by prior bDMARD exposure (yes or no) and geographic region.

See Section 5.5.3 for details.

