4.2 Overall Study Design and Plan

This is a Phase 3 multicenter study that includes two periods. Period 1 is a 48-week randomized, double blind, parallel-group, placebo-controlled and active comparator-controlled period designed to compare the safety and efficacy of Upadacitinib 15 mg QD versus placebo and versus ADA for the treatment of signs and symptoms of subjects with moderately to severely active RA who are on a stable dose of MTX and have an inadequate response to MTX (MTX-IR). Period 1 is also designed to compare the efficacy of Upadacitinib 15 mg QD versus placebo for the prevention of structural progression. Period 2 is a long-term extension to evaluate the safety, tolerability and efficacy of ABT-494 15 mg QD in subjects with RA who have completed Period 1.

The study is designed to enroll approximately 1500 subjects at approximately 510 study centers worldwide to meet scientific and regulatory objectives without enrolling an undue number of subjects in alignment with ethical considerations. Therefore, if the target number of subjects has been enrolled, there is a possibility that additional subjects in screening will not be enrolled.

The study duration includes a 35-day screening period; a 48-week randomized, double-blind, parallel-group, placebo-controlled and active comparator-controlled treatment period (Period 1); a long-term extension period (blinded until the last subject completes Period 1) (up to 5 years) (Period 2); a 30-day follow-up period (call or visit); and a 70-day follow-up call.

Subjects who meet eligibility criteria will be randomized in a 2:2:1 ratio to one of three treatment groups:

- Group 1: Upadacitinib 15 mg QD (N = 600)
- Group 2: Placebo (N = 600)
- Group 3: ADA (40 mg every other week [eow]) (N = 300)

Subjects will receive both oral study drug QD (either Upadacitinib 15 mg or matching placebo) and subcutaneous study drug EOW (either ADA 40 mg or matching placebo) until the study is unblinded.

Randomization is stratified by prior exposure to bDMARD (yes/no) and geographic region.

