9.2.2 Sensitivity Analysis of Primary Efficacy Variables

The primary analysis for point estimate and CI will be repeated using Observed Cases without any imputation as a sensitivity analysis. This will be conducted on the FAS based on randomized treatment groups.

Supportive NRI analysis will also be conducted on the Per Protocol Analysis Set.

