For binary endpoints, frequencies and percentages will be reported for each treatment group. Similar analyses as for the primary endpoint will be conducted. Additionally, for ACR50 response rate at Week 12, analysis will be conducted to test the non-inferiority of Upadacitinib versus ADA using the 95% confidence interval of treatment difference against a non-inferiority margin of 10% for US/FDA regulatory purposes. Similar non-inferiority analysis will be conducted for LDA based on DAS28 (CRP) at Week 12 with a 10% margin for EU/EMA regulatory purposes. Superiority of Upadacitinib vs ADA will also be tested using the Cochran-Mantel-Haenszel test adjusting for stratification factor prior bDMARD use.

For the major RA continuous endpoints DAS28 and HAQ-DI change from baseline, statistical inference will be conducted using analysis of covariance (ANCOVA) coupled with MI for missing data handling. Specifically, the ANCOVA model will include treatment as the fixed factor, and the corresponding baseline value and the stratification factor prior bDMARD use (Yes/No) as the covariates. For other continuous endpoints, statistical inference will be conducted using the MMRM model as described in Section 9.1.2, with the main stratification factor being prior bDMARD use (Yes/No). From both the MI and MMRM analyses, the LS mean and 95% CI will be reported for each randomized treatment group; the LS mean treatment difference and associated 95% CI and p-value will be reported comparing the Upadacitinib 15 mg group with the placebo group. For change from baseline in patient's global assessment of pain and change from baseline in HAQ-DI at Week 12, superiority of Upadacitinib vs ADA will also be tested.

Analyses for the mTSS-based key secondary endpoints are described in Section 9.3.2.

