
Binary Endpoints:
 
 • ACR50/70 response at Week 12 • ACR20 response at Week 12^b • LDA as measured by DAS28(CRP) at Week 12 • CR as measured by DAS28(CRP) at Week 12^a • LDA as measured by CDAI at Week 12 • ACR50 response at Week 12 (superiority of Upadacitinib vs ADA)^a 	
 • Point estimate and 95% CI of the response rate for each treatment group. The 95% CI will be based on normal approximation. • Point estimate, 95% CI and p-value for the treatment comparison between Upadacitinib group and the comparator groups using the Cochran-Mantel-Haenszel test adjusting for stratification factor prior bDMARD use. The 95% CI will be based on normal approximation. • Imputation: NRI for primary analysis and OC for sensitivity analysis • Analysis Set: FAS

Binary Endpoints (Non-inferiority of ABT-494 vs ADA):
 
 • ACR50 response rate at Week 12^a • Proportion of subjects achieving LDA based on DAS28(CRP) ≤ 3.2 at Week 12^b 	
 • 95% confidence interval of treatment difference against a non-inferiority margin of 10%. • Imputation: NRI for primary analysis and OC for sensitivity analysis • Analysis Set: FAS

Table 5. Summary of Efficacy Variables and Corresponding Analyses for Efficacy Analysis by Week 12 (Continued)

Efficacy Variables	Analysis Method
Key Secondary Variables (Upadacitinib Versus Placebo if not Otherwise Specified) (continued)	

Continuous Endpoints:
 
 • Change from baseline in DAS28(CRP) at Week 12 • Change from baseline in HAQ-DI at Week 12 • Change from baseline in HAQ-DI at Week 12 (superiority of Upadacitinib vs ADA).^a 	
 • LS mean, and 95% CI within each treatment group and LS mean, 95% CI and p-values between Upadacitinib group and the comparator groups using ANCOVA model with treatment, prior bDMARD use and baseline value as covariates. • Imputation: MI • Analysis Set: FAS

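### Geographic region stratifies randomisation, but no legible primary or key secondary model in the SAP adjusts for it, which makes the tests slightly conservative

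*SAP*

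**What the plan says.** Protocol 8.3 has subjects randomised 2:2:1, "stratified by prior bDMARD exposure (yes or no) and geographic region". SAP 4.2 agrees: "Randomization is stratified by prior exposure to bDMARD (yes/no) and geographic region".

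For the primary endpoint, Protocol 8.1.4.1.1 says that the "Cochran-Mantel-Haenszel test adjusting for main stratification factors will be used", without naming those factors. The SAP narrows this to one factor:

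- **Primary endpoint (SAP 9.2.1):** compared with placebo "using the Cochran-Mantel-Haenszel test adjusting for stratification factor prior bDMARD use".
- **Other binary endpoints (SAP 9.2.3):** "Similar analyses as for the primary endpoint will be conducted".
- **DAS28 and HAQ-DI (SAP Table 5):** analysed "using ANCOVA model with treatment, prior bDMARD use and baseline value as covariates".
- **Other continuous endpoints (SAP 9.2.3, Table 5):** an MMRM in which prior bDMARD use is named as the main stratification factor.
- **Week 26 mTSS and no radiographic progression (SAP 9.3.2):** ANCOVA and CMH, each adjusted for prior bDMARD use only.
- **Non-inferiority against adalimumab (SAP Table 5):** a 95% interval against a 10% margin, with no covariate named.

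Under SAP 9.2.2 the primary analysis is "repeated using Observed Cases without any imputation as a sensitivity analysis", and NRI is rerun on the Per Protocol set. Neither adds region. Region appears otherwise as a baseline characteristic (SAP 6.1) and as a subgroup factor for the primary endpoint (SAP 9.2.6). The subgroup display has estimates and intervals but no p-value, and a variable is dropped if any of its categories has fewer than 150 subjects.

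**The concern.** When randomisation balances a prognostic factor and the analysis ignores it, the treatment estimate varies less than its standard error claims. The between-region variance stays in the error term. Tests then reject less often than their nominal level, and intervals are a little too wide.

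What is at stake is some precision, and it matters only where power is not already saturated. One such endpoint is change in mTSS at Week 26, planned at about 90% power and ranked second in the US sequence and first in the EU sequence. Under the step-down rule a miss there blocks every lower-ranked claim. The other is superiority over adalimumab, for example ACR50 at US rank 11.

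The trial already collects region and randomises by it, so using it in the models costs very little.

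**Working it through.** **Inputs from the documents (SAP 4.3).** Arms of 600/600/300, or 540/540/270 after 10% dropout; two-sided 0.05. ACR20 59% vs 37%; CR 25.5% vs 6.2%; mTSS difference 0.39 with SD 2; ACR50 or LDA 40% vs 35% with margin 10%.

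**Inputs assumed.** The documents give no regional rates and do not state which region levels randomisation used. The illustration takes six equal regions, rates spread evenly over ±10 or ±15 points, and 20% bDMARD-experienced subjects (the enrolment cap). Collapsed strata means one stratum per region for bDMARD-naive subjects and one pooled stratum for bDMARD-experienced subjects.

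**1. The plan's own figures.**
- mTSS: SE = 2 × sqrt(2/540) = 0.1217; 0.39/0.1217 = 3.204; Φ(3.204 − 1.96) = 89.3%, against about 90% stated.
- ACR20 and CR: above 99.9%.
- Non-inferiority: SE = sqrt(0.35×0.65/270 + 0.40×0.60/540) = 0.0359; Φ(0.15/0.0359 − 1.96) = 98.7%.

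All stated figures are met. None of these formulas uses strata, so they neither support nor contradict the point.

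**2. Type I error for ACR20.** With region balanced but unadjusted, alpha = 2 × (1 − Φ(1.96/sqrt(1 − R²))), where R² = (between-region variance)/(p(1 − p)) and p(1 − p) = 0.37 × 0.63 = 0.2331.
- ±10 points: variance (0.10² + 0.06² + 0.02²)/3 = 0.00467; R² = 0.020; alpha = 4.77%.
- ±15 points: variance (0.15² + 0.09² + 0.03²)/3 = 0.0105; R² = 0.045; alpha = 4.49%.

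Simulation (540 vs 540, 200,000 trials; Monte Carlo standard error about 0.05 points):

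| Spread | CMH, bDMARD only | CMH, collapsed strata |
|---|---|---|
| ±10 | 4.74% | 5.02% |
| ±15 | 4.43% | 4.90% |

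With three or four regions, the bDMARD-only figure is 4.7–4.8% at ±10 and 4.3% at ±15. With unequal regions it is 4.8% and 4.5%. Primary power is 100.0% under both methods.

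**3. ACR50 superiority over adalimumab** (40% vs 35%, 540 vs 270, 300,000 trials). Power rises from 27.6% to 28.2% at ±10 and from 27.4% to 28.7% at ±15.

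**4. mTSS.** Suppose region explains 3% of the variance (assumed).
- Adjusted: Φ(3.204/sqrt(0.97) − 1.96) = 90.2%.
- Unadjusted but balanced: Φ((3.204 − 1.96)/sqrt(0.97)) = Φ(1.263) = 89.7%.

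The gain is about 0.5 points.

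**5. Non-inferiority interval.** Stratifying it by region was tested with a Mantel-Haenszel risk difference and Sato variance on the collapsed strata.
- Planned power: 98.6–98.8% crude, 98.7–98.9% stratified.
- One-sided error at the margin (25% vs 35%): 2.57% and 2.40% crude, 2.68% and 2.63% stratified, at ±10 and ±15.
- Crude versus bDMARD-stratified, the choice that the text leaves open, changes the verdict in 0.04–0.3% of trials at 35%/35% and in 0.003–0.022% at 40%/35%.

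**The case against.** The best defence is that the planned analysis is valid, pre-specified and slightly conservative, so what remains is efficiency. That stands, and it is why the point is minor. It does not account for leaving out a randomisation factor without a reason, or for having no sensitivity analysis that includes it.

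Sparse strata are a plausible unstated reason. The 20% cap allows at most 60 bDMARD-experienced subjects among 300 on adalimumab: 10 per region if six regions are equal, 3 in a region with 5% of subjects. This argues against fully crossed CMH strata. It does not argue against collapsed strata or a region main effect in ANCOVA and MMRM.

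Parts of the MMRM and multiple imputation definitions in SAP 9.1.2 are blacked out. The absence of a reason can therefore be asserted only for the visible text, and region in the imputation model cannot be ruled out. The analysis models themselves are legible.

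Region is also not ignored, because the subgroup display is planned. That display checks consistency of effect and is not an adjusted analysis.

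**Conclusion.** The point holds as a minor one. Region is a randomisation factor, no legible primary or key secondary model uses it, the visible text gives no reason, and no sensitivity analysis fills the gap. The loss is a few tenths of a percentage point of alpha on ACR20, about half a point to just over one point of power on ACR50 superiority, and about half a point on mTSS. These sizes rest on the assumed regional spreads and the assumed 3% of variance. A wider spread would enlarge them.

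A reader might infer more, and four stronger readings fail:

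- **A protocol–SAP conflict.** The protocol speaks of main stratification factors without naming them, and the SAP says which one it means.
- **Inflated false positives or wrong power figures.** The error runs in the conservative direction, and the stated power figures reproduce.
- **An mTSS gain of 0.9 points, from 89.3% to 90.2%.** The 89.3% applies when region explains nothing. At 3% the unadjusted figure is 89.7%.
- **A need to stratify the non-inferiority interval by region.** In the illustration this gains about 0.1 point of planned power and moves the error at the margin above 2.5%.

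**What to change.** In SAP 9.2.1, 9.2.3, 9.3.2 and Tables 5 and 6:

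1. Add region as a fixed factor to the ANCOVA and MMRM models, including the Week 26 mTSS ANCOVA.
2. Stratify the superiority CMH tests by prior bDMARD use and region, with a pre-specified collapsing rule for sparse cells. One option is to pool bDMARD-experienced subjects over regions. Use, and name, the region levels applied in randomisation. The six categories in SAP 6.1 and Table 4 are not stated to be those levels.
3. Leave the non-inferiority interval method as planned, and state whether it is crude or stratified by prior bDMARD use.

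If adjustment for prior bDMARD use alone stays primary, give the reason in a sentence and add a region-stratified sensitivity analysis of the primary endpoint.

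The cost is SAP wording and one class variable, settled before the Week 26 database lock, the deadline that Protocol 8.1 sets for finalising the SAP. The downside is sparse bDMARD-experienced cells, which the collapsing rule handles, and slightly more model specification.
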